Laboratory tests include Hematology, Chemistry, Urinalysis with Microscopic Assessment and other routine assessments. Exploratory renal laboratory tests will also be done at visits specified in section 6.3.6.2. Also See Section 6.3.6.2 for information on all routine laboratory protocol assessments during the Treatment Phase.

ADAS-cog including: immediate word recall, following commands, constructional praxis, object/finger and naming, ideation praxis, orientation, word recognition, recall of test instructions, comprehension, word finding difficulty, and spoken language difficulty.

Executive Function Test includes: Color Trails (A & B), Category and Letter Fluency and Digit Span (Forwards and Backwards)

Pharmacokinetic trough levels will be collected at all visits & non trough levels will be collected every 6 months.

A subset of subjects at specified sites will complete 1 intensive 24-hour PK assessments after 6 weeks on treatment prior to the Week 104 Visit.

A Sample of CSF for PK will be collected at all time points that CSF is collected, after randomization.

q To achieve the most accurate assessment of the peak pharmacodynamic effect of BMS-708163 on CSF amyloid levels, at the Week 104 lumbar puncture must be completed 8-12 hours post dosing with study drug (peak CSF concentrations). The lumbar puncture should be performed at approximately the

same time of day as the baseline procedure. If the timing of the subject's daily dosing is changed to conform to the peak CSF LP measurement requirements, the subject must be dosed at the same time each day for a minimum of 10-days prior to the scheduled LP. This will ensure that the LP reflects the peak pharmacodynamic effects of study medication on CSF amyloid prior to the LP procedure.

If notch-related AEs are suspected additional immunophenotyping, TFF3 may be obtained for purposes of clinical correlation.

s Patient-reported Outcomes in Cognitive Impairment (PROCOG) outcomes measures (for US sites ONLY).

Table 6.1-3: Flow Chart for Pa	or Protocol CN156018 - Observational Cohort	nal Cohort	
	Observational Cohort Assessments	ort Assessments	
Procedure	Baseline	Every 12 Weeks (± 7 days)	Protocol Section
Assessments			
Assessment of Progression to Dementia	X	X	6.4.2.1
CDR-SB	X	X	6.4.2.2
MMSE		X	6.4.3.1
Neuropsychiatric Inventoy Questionnaire (NPI-Q)	×	X	6.4.3.2
ADAS-COG (ADNI Modified)	×	X	6.4.3.6
Executive Function Tests	×	X	6.4.3.7
ADCS-MCI-ADL	×	X	6.4.3.10
Free & Cued Selective Recall Reminding test		X	6.4.3.8
Montreal Cognitive Assessment (MoCA)		X	6.4.3.3
Sheehan Suicidality Tracking Scale (STS)	X	X	6.3.8.1
Columbia-Suicide Severity Rating Scale (C-SSRS)		X	6.3.8.2
Safety and Volumetric Head MRI	X	$X^b$	6.4.4.5
Concomitant Medication Tracking	X	X	5.5

All Screening assessments must be completed and the subject must meet all inclusion/exclusion criteria (with the exception of the  $A\beta42$  level of < 200 pg/mL or a Total Tau/A $\beta42$  ratio of  $\geq 0.39$ ) to be eligible for the Observational Cohort. Refer to Section 6.4.4.8 for additional details.

77

b On-study MRI should be done at the week 60 visit, or the next scheduled visit for subjects who have surpassed week 60.

<sup>c Only CNS acting medications are required to be captured for Observational Cohort participants.

Flow Chart for Protocol CN156018 - Long-Term Follow-up and Post Treatment/Study Termination Safety Follow-Up Visits Table 6.1-4:

Procedure	LTFU Every 12 Weeks (+ 7 days)	4 Week Post Txt	12 Week Post Txt	24 Week Post Txt a	Protocol Section
Assessments					
Assessment of Progression to Dementia	X		X		6.4.2.1
CDR-SB	X		X		6.4.2.2
MMSE	X		X		6.4.3.1
ADAS-COG	X		X		6.4.3.6
Geriatric Depression Scale	X		X		6.4.3.5
DSM-IV-TR	X		X		6.4.2.1
NINCDS-ADRDA	X		X		6.4.2.1
ADCS-MCI-ADL	X		X		6.4.3.10
Vital Signs	X	X	X		6.3.5
Physical Measurements	X	X	X		6.3.5
Routine Safety Laboratory Tests, including exploratory renal laboratory tests (central laboratory)	×	X	X		6.3.6.2
Renal (Cystatin C and Urine Microalbumin)			X		6.4.4.2
Comprehensive Structured Skin Examination			X		6.3.4
Comprehensive Skin Examination				X	6.3.4
12 Lead ECG (central laboratory)	X				6.3.1
Adverse Event Assessments	X	X	X		7.1
Concomitant Medication Tracking	X	X	X		5.5

a Post Treatment/Study Termination Safety Follow-up Visit at 24 Weeks will only include a comprehensive skin examination by a dermatologist (or dermatologic physician's assistant in the United States).

b Vital Signs include sitting and standing orthostatic pulse and blood pressure measurements.

c Weight measurements are to be completed during Long-term Follow-up.

d Only CNS acting medications are required to be captured for Long-term Follow-up participants.

#### 8 STATISTICAL CONSIDERATIONS

# 8.1 Sample Size Determination

The primary endpoint of this study is safety and tolerability. The sample size of 135 subjects per group is chosen empirically rather than based on the statistical power consideration. However, it should be noted that with 135 subjects per dose group, the probability of observing at least one specific AE is satisfactorily high at each dose group if the true event rate of that AE is within the commonly observed ranges, as shown in Table 8.1-1 with a list of assumed true event rates. For example, the probability of observing at least 1 specific AE is 98% at each dose group if the true event rate of that AE is 3% (Table 8.1-1). Table 8.1-2 shows the probability of observing at least one event difference assuming different event rates for each treatment group. In addition, the 95% exact confidence interval of 10% (13 events out of 135 subjects) event rate in each group is (0.05, 0.16).

Table 8.1-1: Probability of Observing a Given Adverse Event

Assumed AE incidence rate	Probability of observing at least 1 AE out of 135 patients a
0.1%	12.6%
0.5%	49.1%
1%	74.2%
2%	93.5%
3%	98.4%

Assumes a distribution of Binomial (n = 135, probability of event given in the first column).

Table 8.1-2: Probability of Observing at Least One Incidence Difference

AE incidence rate (%) for Placebo		AE incidence rate (%) for Active						
		0.1	0.5	1	2	3		
	0.1	22.3%						
	0.5	51.4%	60.9%					
	1	73.2%	71.8%	74.1%				
	2	92.0%	87.0%	83.2%	82.2%			
	3	97.6%	95.0%	90.9%	86.1%	85.6%		

# 8.2 Populations for Analyses

• The **Enrolled Sample** comprises all subjects who sign informed consent and obtain an enrollment number

• The **Randomized Sample** comprises all subjects who are randomized in the double-blind treatment phase.

• The **Safety Sample** comprises all subjects in the Randomized Sample who take at least one dose of double-blind study medication as indicated on the study therapy form.

All safety analyses will be performed on the Safety Sample, except for listings of deaths and serious adverse events (SAEs), which will use the Enrolled Sample. For safety analyses, if a subject receives a treatment other than one to which he or she was randomized, this subject will be analyzed as treated (based on the first medication kit number received after randomization).

All efficacy analyses will be performed on the Randomized Sample, unless otherwise specified. All efficacy analyses will be performed at Baseline (if evaluated at baseline), at endpoint (104 week treatment period), and at each specified study month. Efficacy analyses will be performed using observed cases. For efficacy analyses, if a subject receives a treatment other than the one to which he or she was randomized, this subject will be analyzed as randomized.

# 8.3 Endpoint Definitions

**Safety endpoints**: Adverse Events, Physical and Neurological Examinations, Vital Signs, Laboratory Assessments, ECGs, and Safety Head MRI findings.

**Clinical endpoints**: CDR-SB, ADAS-cog, NPI, ADCS-MCI-ADL and rate of progression from prodromal AD to mild/moderate AD.

**Biomarker endpoints**: CSF biomarkers (A $\beta$ -40 and A $\beta$ -42, total Tau, total Tau/A $\beta$ 42 ratio and phosphorylated Tau) and volumetric brain magnetic resonance imaging measurements, and PET

**Pharmacokinetic Measures**: Pharmacokinetic trough plasma concentrations of BMS-708163 (and metabolites if warranted) will be determined in all subjects at all visits during the treatment phase starting at the Week 2 visit. A subset of subjects will complete intensive 24-hour PK sampling (after 6 weeks on treatment and prior to the Week 104 visit). Free BMS-708163 may be determined in each subject at the highest expected concentration using ex vivo plasma protein binding techniques, if warranted.

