# 2.3 Exploratory Objectives

1) To explore drug effects on progression to dementia (based on confirmed progression using DSM-IV criteria)

- a) To explore effects of BMS-708163 on brain atrophy rate as measured by volumetric MRI
- b) To explore and prospectively characterize effects the Clinical Dementia Rating scale (including the CDR-Sum of Boxes score and CDR global score), an instrument designed to measure the severity of cognitive symptoms in daily life, as part of the natural course (in placebo patients) and potential impact of BMS-708163
- c) To explore the correlation of APOE status with BMS-708163 pharmacodynamic (PD) effects (such as on biomarkers and cognition)
- d) To explore Aβ42 CSF Screening cut-off value of > 200 pg/mL versus < 200 pg/mL and Total Tau/AB42 ratio ≥ 0.39 with regard to progression rates and biomarker changes in both the randomized and the non-randomized, observational cohort of subjects
- e) To explore the pharmacodynamic effects of BMS-708163 on CSF biomarkers linked to mode of action (A $\beta$ 38, A $\beta$ 40, A $\beta$ 42), and putative biomarkers of neurodegeneration (total Tau, phosphorylated Tau) and lipid peroxidation (isoprostanes) in AD
- f) To explore the pharmacodynamic effects of BMS-708163 on Cognition as assessed by an Executive Function Test Battery and the ADAS-cog
- g) To explore the pharmacodynamic effects of BMS-708163 on Function in daily living as assessed with the Alzheimer's disease Collaborative Study Activities of Daily Living scale (ADCS-MCI-ADL)
- h) To explore the pharmacodynamic effects of BMS-708163 on progression on the Global Clinical Dementia Rating (CDR global) (ie, progression to a global score of 1)
- i) To explore effects of BMS-708163 on brain amyloid content as measured via PET-amyloid imaging (AV-45) in a subset of subjects at specified sites
- j) To explore the pharmacodynamic effects of BMS-708163 on the subject-reported Outcomes in Cognitive Impairment (PROCOG), an instrument designed to assess severity of impairment and impact on subjects
- k) To assess Notch-mediated (safety related) effects of BMS-708163 on:
  - TFF3 plasma concentrations and its association with gastrointestinal safety signals
  - Lymphocyte mRNA levels of HES-1 and its association with clinical safety signals
  - The immune system (lymphocyte subpopulations; immunoglobulin serum levels)
- 2) To characterize pharmacokinetics (PK) and its relationship with pharmacodynamic (PD) effects:

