All subjects will be randomly assigned in a double-blind manner to one of the following treatment groups: placebo or 50 mg BMS-708163 once daily. Treatment allocation will be balanced by symptomatic co-medication (ChEI): yes/no; Apolipoprotein E (APOE) Status (yes+/no-), consent for PET Imaging (yes/no) and consent for intensive PK assessments (yes/no).

All subjects will be treated with 50 mg during the study. Downward titration to 25 mg/day of BMS-708163 based upon the investigator's clinical judgment will only be allowed to manage limiting adverse events that emerge during the study. It is recommended that if down-titration does occur, the investigator consider a re-challenge to the highest tolerated dose for the subject to maximize A $\beta$  reductions. If the investigator does not attempt to re-challenge to the highest-tolerated dose, the investigator should contact the BMS medical monitor with the clinical rationale for not re-challenging at the higher dose. For the purposes of down-titration for tolerability issues, a dose range of 25 mg - 50 mg per day will be allowed during the treatment phase. A low dose of 25 mg per day is estimated to provide approximately > 10% A $\beta$  reduction, a level of reduction that may still provide a potentially meaningful reduction in brain A $\beta$  levels

All subjects will have trough PK assessments starting at the Week 2 visit and at all subsequent visits during the treatment period. An additional post-dose PK assessment will be completed at selected visits. At the time of CSF sample collection, both a blood and CSF sample will be collected for plasma and CSF PK analysis. These sample collections are outlined, in the Time & Events Schedule. A subset of subjects, at selected sites, will also complete one intensive 24-hour PK assessment on a day after they have been on treatment for 6 weeks and at a stable dose for at least two weeks (see Section 6.5.5.1). Safety and PD assessments will be performed as outlined in the Time & Events Schedule (see Section 6.1).

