# 2) Target Population

- c) Subject meets prodromal Alzheimer's disease criteria as defined by:
  - i) Memory complaint by subject or study partner that is verified by a study partner.
  - ii) Abnormal memory function documented by at least 1 of the 4 following criteria:
    - (1) scoring below the education adjusted cutoff on the Logical Memory II subscale (Delayed Paragraph Recall) from the Wechsler Memory Scale Revised (the maximum score is 25):
      - (a) less than or equal to 8 for 16 or more years of education.
      - (b) less than or equal to 4 for 8 15 years of education.
      - (c) less than or equal to 2 for 0 7 years of education. **OR**
    - (2) Free and Cued Selective Reminding Test (FCSRT) Total Recall score of  $\leq$  39 **OR**
    - (3) Free and Cued Selective Reminding Test (FCSRT) Free Recall score of  $\leq 24$  OR
    - (4) Free and Cued Selective Reminding Test (FCSRT) Delayed Free Recall score of  $\leq 8$ .
- d) CSF A $\beta$ 42 levels below 200 pg/mL or Total Tau / A $\beta$ 42 ratio of  $\geq$  0.39. Additionally, subjects who meet all other inclusion/exclusion criteria with the exception of the CSF criteria above, may be eligible to be followed in a non-randomized, observational cohort to assess progression rates [see Section 6.4.4.8]);
- e) Mini-Mental State Exam score between 24 and 30 (inclusive);
- f) Clinical Dementia Rating global score must be = 0.5 at Screening and Baseline **and** the Memory Box score must be at least 0.5 at both Screening and Baseline;
- g) Subjects must have an MRI performed during the screening period, prior to randomization, to allow the results to be available at the baseline visit. Results will be centrally read. To be eligible for the study the MRI results must:
  - i) Be normal (commensurate with age) or demonstrate atrophy consistent with an Alzheimer's disease diagnosis;
  - ii) Reveal no more than mild to moderate white matter disease;
  - iii) Up to 2 lacunar infarcts are acceptable however, no lacunes are permitted in the anterior thalamus, genu of internal capsule, or basal forebrain;

CN156018 Clinical Protocol

- iv) Reveal no cortical infarcts;
- v) Reveal no more than four microbleeds. Note: if an MRI scanner with a field strength > 1.5 T is used, a higher number of microbleeds will be acceptable as determined by the central neuroradiologist.

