- at least 10 days prior to the LP procedure. To achieve the most accurate assessment of the peak pharmacodynamic effect of BMS 708163 on CSF amyloid levels, all lumbar punctures must be completed 8 - 12 hours post dosing with study drug (peak CSF concentrations). The lumbar punctures will either be done in the morning following the last dose of study medication taken the evening prior or in the late afternoon following the morning dose. Ideally, the timing of the lumbar punctures will be consistent with the timing of the initial baseline lumbar puncture. If the timing of the subject's daily dosing is changed to An additional PK assessment will be obtained at the time of each lumbar puncture. An optional peak dosing CSF collection will occur after Week 2 for those subjects agreeing to an additional LP. This additional LP can be performed at any time after week 2 as long as the subject is on a stable dose of study drug for conform to the peak CSF LP measurement requirements, the subject must be dosed at the same time each day for a minimum of 10-days prior to the scheduled LP. This will ensure that the LP reflects the peak pharmacodynamic effects of study medication on CSF amyloid prior to the LP procedure.
- If notch-related AEs are suspected additional immunophenotyping, TFF3, and HES1 notch biomarkers may be obtained for purposes of clinical correlation.
- Patients that are unable (due to existent medical condition, ie, pacemaker or ICD device) or unwilling to have a head MRI completed will be excluded from the study. Screening MRI may be performed at any time between the Screening and Baseline visits. Results from the centrally read MRI must be received by the site PRIOR to randomization (Baseline) to ensure all inclusion criteria are meet. Refer to Section 6.4.5 for more details.
- Patient-reported Outcomes in Cognitive Impairment (PROCOG) outcomes measures (for US sites ONLY).

89

Table 6.1-2:		Ĭ.	low	Ch	art	for	Proto	col C	Flow Chart for Protocol CN156018	)18											
							Tre	atment F	Treatment Phase (Week 32 - Week 220 a ) End of Week (± 7 days)	(Week	< 32 - V = 7 days	Week 2	(20 a )					Sa. Fol	Safety Follow- up	Un- scheduled (Pro- gression Assess- ment)	
Procedure	32	4	56 68		80 92		104 / DC b	116	128	140	152	164	176	188	200	212	220/ DC/ End of Trt	+	+12	Uq	Protocol Section
12 Lead ECG (central laboratory)	×	×	×	×	×	×	×	×	×	×	×	×	×	×	×	×	×				6.3.1

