Pearson's correlation coefficient will be used to estimate the linear relationship between clinical outcomes such as CDR-SB with biomarkers at study months when both measurements are available. Post-treatment follow-up data from the safety follow-up phase will be considered in sensitivity analyses. Trending of clinical rating scales during the active treatment period differing

from those after discontinuation from treatment will be investigated. Number of progressions after study medication discontinuation will also be tabulated, but will not be adjudicated.

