# 8.4.8 Other Analyses

#### 8.4.8.1 Biomarker Analyses

The mean change from baseline to each scheduled visit in the proposed biomarker measures (CSF biomarkers, plasma biomarkers and Volumetric MRI) will be analyzed based on Safety Sample. The analysis will make use of ANCOVA model, controlling for key covariates (APOE4 genotype, and concurrent AD medication use) and adjusting for corresponding baseline.

Specifically, for plasma TFF3 or CSF and plasma A $\beta$ 40 and A $\beta$ 42, the ANCOVA model will be applied to the log-transformed percentage of baseline measures. If multiple post-treatment time points were measured, a linear mixed effect model with fixed dose effect and time effect (repeated measures) will be used for the analysis.

For whole blood mRNA genes (HES-1), the gene expression level will be normalized to an internal housekeeping gene (eg, GAPDH) before applying statistical analysis. The change from baseline of the normalized gene expression levels will be fitted into the ANCOVA model.

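### The total tau/Aβ42 ratio is an on-treatment change endpoint although the drug lowers its denominator, and the biomarker–CDR-SB correlations carry no treatment adjustment

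*Protocol*

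**What the plan says.** **The ratio as an endpoint.** The biomarker endpoints in Section 8.3 are CSF Aβ40, Aβ42, total tau, the total tau/Aβ42 "ratio and phosphorylated Tau) and volumetric brain magnetic resonance imaging measurements", and PET. Section 8.4.8.1 then states: "The mean change from baseline to each scheduled visit in the proposed biomarker measures (CSF biomarkers, plasma biomarkers and Volumetric MRI) will be analyzed". It uses ANCOVA, or a mixed model where there are several time points. It does not name the ratio, but the ratio is one of the CSF biomarkers that Section 8.3 defines.

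**The drug's action on the denominator.** Objective 1e in Section 2.3 reads "To explore the pharmacodynamic effects of BMS-708163 on CSF biomarkers linked to mode of action" and puts Aβ38, Aβ40 and Aβ42 in that group. It names total tau and phosphorylated tau as the putative neurodegeneration markers and does not mention the ratio. The dosing text in Section 4.1 says "A low dose of 25 mg per day is estimated to provide approximately > 10" per cent Aβ reduction. The notes to the flow charts in Section 6.1 time lumbar punctures to capture the "peak pharmacodynamic effect of BMS 708163 on CSF amyloid levels".

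**The ratio at entry.** Inclusion criterion d in Section 4.2.1 requires "42 levels below 200 pg/mL or Total Tau"/Aβ42 of at least 0.39. Before treatment, low Aβ42 or a high ratio is thus the CSF evidence for prodromal AD.

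**The correlations.** Section 8.4.3 states: "Pearson's correlation coefficient will be used to estimate the linear relationship between clinical outcomes such as CDR-SB with biomarkers at study months" when both are measured. It mentions neither arm nor adjustment. Section 8.2 makes the Randomized Sample the default for efficacy analyses.

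**The concern.** A ratio whose denominator is the drug's target has a different meaning on treatment than at screening. Before dosing, both parts reflect disease. On dosing, the denominator also reflects target engagement, and sampling is timed to when that effect is largest. A between-arm difference in change of the ratio is then a mixture of engagement and any effect on tau.

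The objectives do not ask for this comparison. The five CSF items in Section 8.3 are the same five as in the secondary objective (Section 2.2), which concerns prediction of progression and is analysed on baseline values. Objective 1d uses the ratio as a screening cut-off. Objective 1e, on drug effects, leaves it out.

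The correlation analysis has a related weakness. Treatment shifts Aβ between arms. If CDR-SB also differs by arm, a single r across both arms combines the within-arm relationship with the between-arm shift. Elsewhere Section 8.4.3 guards against this: the Cox model includes treatment, and the Aβ42 cut-off analysis uses only placebo and observational subjects. The Pearson analysis has neither safeguard.

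At stake is the interpretation of exploratory biomarker results.

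**Working it through.** The plan gives no figure for either quantity, so there is none to reproduce.

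**Inputs**
- Aβ reduction: above about 10% at 25 mg/day (Section 4.1). The available text gives no figure for 50 mg/day, so 20% to 40% is assumed. The 10% is stated for Aβ in general; applying it to CSF Aβ42 is also an assumption.
- Two arms of 135 (Section 8.1), so equal allocation.
- Arm shifts in SD units: not in the protocol. Assumed 1 to 2 SD in the biomarker and 0.3 to 0.5 SD in CDR-SB.

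**Step 1: the ratio with tau unchanged.** If Aβ42 falls by a fraction a, the ratio is multiplied by 1/(1 − a).
- a = 0.10: 1/0.90 = 1.11, a rise of 11%
- a = 0.20: 1/0.80 = 1.25, a rise of 25% (assumed a)
- a = 0.30: 1/0.70 = 1.43, a rise of 43% (assumed a)
- a = 0.40: 1/0.60 = 1.67, a rise of 67% (assumed a)

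**Step 2: the ratio when tau falls too.** If tau falls by a fraction t, the multiplier is (1 − t)/(1 − a).
- a = 0.10, t = 0.10: 0.90/0.90 = 1.00. The fall in tau is invisible.
- a = 0.10, t = 0.05: 0.95/0.90 = 1.056. The ratio rises although tau has fallen.

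On the log scale, the change in the ratio is the change in tau minus the change in Aβ42. It carries nothing about treatment that the two separate endpoints do not.

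**Step 3: correlation across both arms.** Let ρ be the within-arm correlation, and dx and dy the arm differences in biomarker and CDR-SB in within-arm SD units. With equal arms:

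pooled r = (ρ + dx·dy/4) / √[(1 + dx²/4)(1 + dy²/4)]

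With ρ = 0:
- dx = 1, dy = 0.3: 0.075/√(1.25 × 1.0225) = 0.066
- dx = 1, dy = 0.5: 0.125/√(1.25 × 1.0625) = 0.11
- dx = 2, dy = 0.3: 0.150/√(2 × 1.0225) = 0.10
- dx = 2, dy = 0.5: 0.250/√(2 × 1.0625) = 0.17

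The sign follows the directions of the two shifts.

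With dy = 0, a true zero stays zero and a true 0.30 only shrinks: to 0.298, 0.291 and 0.268 for dx = 0.25, 0.5 and 1. With ρ = 0.30, dx = 1 and dy = −0.3 or +0.3, pooled r is 0.199 or 0.332.

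**Step 4: cost in precision of separating arms.** On Fisher's z scale the 95% half-width is 1.96/√(n − 3).
- n = 270: 1.96/√267 = 0.12
- n = 135: 1.96/√132 = 0.17

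These are best cases, since they assume every randomised subject contributes both measurements.

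**The case against.** Several points on the other side stand.

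- **Reading a rise as worsening.** A reader might infer that target engagement will be reported as worsening AD pathology. No section says so and no decision rule uses the on-treatment ratio. Objective 1e already separates mode-of-action markers from neurodegeneration markers.
- **Crossing the entry threshold.** A reader might note that at a 10% Aβ42 fall, a subject with a ratio of 0.39 × 0.90 = 0.351 would reach 0.39. This has no consequence: 0.39 and 200 pg/mL are screening values, and nothing applies them again on drug.
- **Components already reported.** Section 8.3 lists Aβ42 and total tau separately, so a rise in the ratio can be traced to its source.
- **Validity.** The randomised comparison is a valid estimate of the drug's effect on the ratio. Only its interpretation is at issue, so the endpoint need not be deleted.
- **Is the ratio in the change analysis at all?** Section 8.4.8.1 does not name it. Its inclusion follows from reading that section with Section 8.3, which is the natural reading but still an inference.
- **Correlations.** Pooling is nowhere stated. It is the default under Section 8.2, and the SAP may settle it. Nor would an arm difference in CDR-SB caused by the drug's effect on Aβ be unrelated to disease.

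These points limit the consequence. They do not remove the ambiguity of the on-treatment ratio or supply the missing treatment adjustment.

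**Conclusion.** The point holds in a limited form.

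Sections 8.3 and 8.4.8.1 together make the ratio an on-treatment change endpoint, and the drug acts directly on its denominator. At the only documented level of reduction, about 10%, the ratio rises by about 11% with tau unchanged. Larger rises depend on assumed reductions. The change in the ratio cannot distinguish target engagement from neurodegeneration and can mask a fall in tau.

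The correlation issue is secondary and modest. From a true zero, the distortion is about 0.07 to 0.17 in absolute size under the assumed shifts, and there is only attenuation if CDR-SB does not differ by arm.

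The documents do not support the stronger conclusion that the trial would report drug action as disease progression. The primary safety objective, the sample size and the Cox analysis of baseline biomarkers, which already includes treatment, are unaffected.

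**What to change.** - **Section 8.4.3:** compute the Pearson correlations within each arm, or as partial correlations adjusted for treatment. Take the placebo arm as the estimate of the disease relationship.
- **Sections 8.3 and 8.4.8.1:** state that the total tau/Aβ42 ratio serves as a baseline predictor and that any post-baseline change in it is pharmacodynamic only. Base conclusions about neurodegeneration on total tau and phosphorylated tau, in line with objective 1e.

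The cost is wording in three sections, with no new data. The downside is wider intervals for within-arm correlations: a half-width of about 0.17 rather than 0.12 on Fisher's z scale, at best. A partial correlation avoids most of that loss but assumes a similar relationship in both arms.
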